2.3 Exploratory Objectives

The exploratory objectives are:

- To determine the effects of sebelipase alfa on lipid parameters
- To assess the effects of sebelipase alfa on achievement of developmental milestones
- To evaluate potential disease-related biomarkers

3 Study Design

3.1 Overview of Study Design and Flow Chart

This is an open-label, repeat-dose, study of sebelipase alfa in infants with rapidly progressive LAL Deficiency. Eligible subjects will receive once weekly (qw) IV infusions of sebelipase alfa for up to 3 years, as described below. All subjects will be evaluated for safety, tolerability, and efficacy. Where feasible, given blood volume thresholds based on subject weight, blood samples will also be collected for analyses of the PK of sebelipase alfa and for an exploratory analysis of potential disease-related biomarkers in this patient population.

All subjects will initiate treatment with sebelipase alfa at a dose 1 mg/kg qw. A dose escalation to 3 mg/kg qw may be considered for a subject who meet specified criteria, as defined below, contingent upon acceptable safety and tolerability of preceding infusions and as approved by the Investigator and Sponsor.

An independent Safety Review Committee (SRC) will oversee safety in this study. The SRC will review available safety data during at least semiannual periodic meetings and on an ad-hoc basis as needed in the event of unanticipated safety findings. Additional details about the SRC review process can be found in Section 7.5.

Subjects who do not tolerate a dose of 3 mg/kg qw may receive a dose reduction to 1 mg/kg qw at the discretion of the Investigator in consultation with the Sponsor and, where appropriate, the SRC. If a subject cannot tolerate a dose of 1 mg/kg qw, despite measures taken to manage any IARs, the subject will be discontinued from the study.

Subjects who are on treatment for at least 96 weeks and have been on a stable dose for at least 24 weeks, may transition to an every other week dosing schedule at the same dose they received on the weekly dosing schedule at the criteria of the Principal Investigator (PI) and in consultation with the Sponsor. If the subject meets the criteria for dose escalation while on the every other week dosing schedule they will either revert back to weekly dosing or if on 1 mg/kg qow increase to 3 mg/kg qow dosing.

Given the severity and life threatening nature of rapidly progressive LAL Deficiency, it is likely that these subjects will be hospitalized during the first several weeks on study. For the subjects who are stable enough to be treated on an outpatient basis, safety follow-up assessments for AEs will be conducted by telephone 24 hours following the first 2 infusions of 1 mg/kg qw and 3 mg/kg qw, as applicable.

Subjects who appear to have an acute illness (e.g., upper respiratory infection or febrile illness) should have their scheduled infusions postponed by up to 2 days (up to 5 days if subject is on a qow infusion schedule) to allow for resolution. If the illness persists for longer than 2 days (5 days if subject is on a qow infusion schedule), the infusion schedule should reset to the next scheduled infusion after the subject's recovery. The Investigator may conduct an unscheduled visit at any time during the study at his/her discretion. Assessments performed at this visit should be symptom directed. Safety laboratory testing may be performed if the Investigator considers it necessary. Repeat laboratory testing may be needed based on results from the

unscheduled laboratory testing. If the subject is discontinued from study treatment at a scheduled visit or at an unscheduled visit, the subject should return no earlier than 7 days after the last dose of IMP for an End of Study assessment.

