4.5 Concomitant Medication and Treatment

A concomitant medication is any drug or substance taken during the study after the informed consent is signed. Any concomitant medications (including over the counter medications, herbal medications, preventive vaccines, vitamins and food supplements), treatments and procedures (including parenteral feeds, surgery, or physical therapy) received by the subject through completion of the follow-up visit, approximately 30 days after the last dose of IMP, must be recorded in the electronic case report form (eCRF). A description of the type of drug or procedure, the amount, duration, reason for administration of drug and the outcome of any procedure must be documented. Adverse events related to the administration of a concomitant medication or the performance of a procedure must also be documented on the AE page of the eCRF.

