8.8.1 Adverse Events

All reported AEs will be listed from the date of written informed consent until the end of participation in this study. Separate listings of deaths, SAEs and IARs will also be provided. The numbers and percentages of subjects experiencing any AE, any SAE, any IAR, any related AE, any related SAE, and discontinuations due to an AE will be tabulated.

The frequency of subjects with treatment-emergent AEs, SAEs, and IARs by system organ class (SOC) and preferred term (PT) (coded using Medical Dictionary for Regulatory Activities [MedDRA®] version 14 or higher) will be tabulated. Frequencies will also be presented by the classifications of severity and causality. In addition, frequency of subjects with AEs, SAEs, and IARs will be presented for time periods spanning the entire course of treatment with sebelipase alfa: from the start of dosing with sebelipase alfa in this study to 3 months after the first dose, >3 to 6 months, >6 to 12 months, >12 to 18 months, >18 to 24 months and >24 months. As appropriate, additional listings, summary tables and graphics will be generated to evaluate IAR frequency and severity over time. A listing of subjects who withdraw from the study due to AEs will be presented, and the incidence of AEs leading to study discontinuation will be summarized.

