Appendix B: Diagnosis and Guidelines for Management of Infusion Associated Reactions

General guidelines for the diagnosis and management of infusion-associated reactions (IARs) are provided below. These guidelines are not intended to be comprehensive. The Investigator should use his/her clinical judgment in the management of IARs in individual subjects participating in this study. In the case of a severe life-threatening reaction, current medical standards for emergency treatment are to be followed.

Symptoms	Action
Mild Common Hyperemia (Flushing) Lightheadedness Nausea Mild chest discomfort (tightness) Less Common Fever and/or shivering Palpitations Headache Irritability (especially in young children)	 Slow infusion rate by 50% Administer oral anti-pyretic and/or antihistamine Decrease infusion rate by a further 25% if symptoms persist If the event resolves, the infusion should continue at reduced rate for a minimum of 30 minutes before infusion is increased to 75% of original rate. If subject tolerates infusion at 75% of the original rate for at least 30 minutes the original rate may be restored for the remainder of the infusion If symptoms continue despite rate reduction stop infusion Pre-treat with oral antihistamine and antipyretic prior (approximately 1.5h) to next infusion e.g., diphenhydramine (1 mg/kg orally) and acetaminophen (15 mg/kg orally)
 Moderate Reaction Hyperemia (flushing) Chest discomfort Itching and/or raised urticarial rash Severe headache Gastro intestinal symptoms, vomiting, diarrhoea, abdominal cramping. 	 Stop infusion Give antihistamine IV and consider IV steroids Consider giving a beta-adrenergic inhaler treatment if appropriate If the event resolves, the infusion may continue at a reduced rate of 50% of the original for a minimum of 30 minutes before the infusion is increased to 75% of the original rate. If the patient tolerates the infusion at 75% of the original rate for at least 30 minutes the original rate may be restored for the remainder of the infusion. If reaction persists despite rate reduction stop infusion Pre-treat with oral antihistamine and antipyretic prior to next infusion

Severe Anaphylactic Reaction

- Clinically significant cardiovascular effects: eg, hypo/hypertension defined as a decline approaching 20-30% of their preinfusion value without alternative etiology (agitation, pain, fluid overload, dehydration)

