#### 7.2.2.2. AEs, SAEs and IARs by System Organ Class (SOC) and Preferred Term (PT)

The frequencies of TEAEs, SAEs, IARs and percentage of patients with events will be tabulated by PT within SOC. Patients are counted once in each SOC and PT. Percentages will be based on the total number of patients in the specific analysis population. SOCs will be listed in order of frequency of occurrence.

Frequencies will also be presented by the classifications of severity and causality. In addition, frequency of AEs, SAEs, and IARs will be presented for time periods spanning the entire course of treatment with SBC-102: from the start of dosing with SBC-102 in this study to 3 months after the first dose; >3 to 6 months; >6 to 12 months; >12 to

Alexion Pharmaceuticals LAL-CL08

18 months; >18 to 24 months; and >24 months. The incidence of AEs leading to study discontinuation will also be summarized.

Summaries of adverse events will be summarized by anti-drug antibody (ADA) status. Subjects who developed ADA vs subjects who did not develop ADA. For subjects who developed ADA, only those AEs reported on or after the first time ADA were identified will be summarized. The number of subjects experiencing any TEAE will be presented overall and by relationship to study drug, with AE specific details presented by SOC and PT, also by relationship to study drug. This table will also be generated for all TESAEs and for all IARs.

Detailed listings of patients who experience AEs, SAEs and IARs will be presented. Detailed listings will include severity and relationship to treatment, seriousness, as well as action taken regarding study treatment, other action taken, and patient outcome. A separate listing of patients who discontinued from the study due to a treatment-emergent AE will also be provided.

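### Infusion reactions are tabulated over unequal periods, on a fixed denominator and with no link to premedication, so a change across periods cannot be interpreted

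*Protocol*

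**What the plan says.** Safety and tolerability are the primary objective (protocol 2.1), and IARs are the adverse events of special interest (protocol 7.1.3).

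- **By period.** Protocol 8.8.1: "frequency of subjects with AEs, SAEs, and IARs will be presented for time periods spanning the entire course of treatment". SAP 7.2.2.2 drops the words about subjects: "frequency of AEs, SAEs, and IARs will be presented for time periods spanning the entire course of treatment with SBC-102". After the first three months the periods are ">3 to 6 months, >6 to 12 months, >12 to 18 months, >18 to 24 months and >24 months". SAP 7.2.2.2 bases percentages on all patients in the analysis population.
- **Premedication.** In Appendix B, the moderate and severe entries both say "Pre-treat with oral antihistamine and antipyretic prior to next infusion" (severe only if dosing resumes). The mild entry has the same instruction with a lead time of about 1.5 hours. Nothing is said about the infusions after the next one, and the appendix calls itself general guidance.
- **Other responses to a reaction.** The infusion rate is slowed (protocol 7.1.3, Appendix B). A child who does not tolerate 3 mg/kg may have the dose reduced (protocol 3.1). A child leaves the study "If a subject cannot tolerate a dose of 1 mg/kg qw, despite measures taken to manage any IARs". That sentence is a discontinuation rule; it matters here only because it takes children out of later periods.
- **What is recorded.** Protocol 4.5 requires "A description of the type of drug or procedure, the amount, duration, reason for administration of drug". SAP 7.1.3.3 tabulates concomitant drugs by ATC class and generic name and lists them with dates. SAP 7.2.1 lists each infusion with its rate and any modification.
- **Optional displays.** Protocol 8.8.1 says that, as appropriate, "additional listings, summary tables and graphics will be generated to evaluate IAR frequency and severity over time". Premedication is not mentioned.

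**The concern.** The planned IAR splits are by SOC and preferred term, severity, causality, period and ADA status. None uses premedication or the number of infusions given in the period. Premedication is started by the outcome being counted, so the mix of premedicated and unpremedicated infusions can shift as treatment goes on. Rate slowing and dose change can shift in the same way.

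The period table also has two faults unrelated to premedication. Its later intervals are longer, so they collect more reactors at the same risk. Its denominator keeps children who have died or withdrawn, so they count as free of reactions.

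The study intends to describe IARs over time. A fall could be taken for growing tolerance of the drug, and a rise for sensitisation, when either may come from the layout of the table or from how reactions were managed.

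**Working it through.** The documents give no IAR rate and no premedication effect, so there is no plan figure to reproduce. The check asks what the planned table would show if a child's tendency to react never changed.

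**Inputs from the documents.** Weekly infusions for up to 3 years and the six periods, hence about 13, 13, 26, 26, 26 and 52 infusions (156 in all).

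**Assumptions.** Risk p per unpremedicated infusion; risk p' per infusion after the first IAR, if premedication is then kept up. All children are alike and stay on treatment.

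**Formulas.**
- Risk at infusion k = p(1−p)^(k−1) + p'[1−(1−p)^(k−1)].
- Share of subjects with at least one IAR in a period covering infusions a+1 to c = 1 − {(1−p)^c + [1−(1−p)^a](1−p')^(c−a)}.

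Example, months 3 to 6, p = 0.10, p' = 0.03: 1 − {0.90^26 + (1 − 0.90^13) × 0.97^13} = 1 − {0.065 + 0.746 × 0.673} = 0.433.

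**Subjects with an IAR (%), the protocol's metric**

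| Assumption | 0–3 | >3–6 | >6–12 | >12–18 | >18–24 | >24 months |
|---|---|---|---|---|---|---|
| p = p' = 0.05 (no effect) | 49 | 49 | 74 | 74 | 74 | 93 |
| p = 0.10, p' = 0.03 | 75 | 43 | 57 | 55 | 55 | 79 |
| p = 0.10, p' = 0.05 | 75 | 55 | 75 | 74 | 74 | 93 |
| p = 0.10, p' = 0.07 | 75 | 65 | 85 | 85 | 85 | 98 |
| p = 0.05, p' = 0 (complete protection) | 49 | 25 | 19 | 5 | 1 | 0 |

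The first row rises although nothing has changed. The next three dip in months 3 to 6, recover and end above where they started. Only complete protection, among these, gives a fall in every period. If the last period is dosed every other week (26 infusions), its 93% in the first row becomes 74%.

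**Expected events per child**, p = 0.10, p' = 0.03: about 0.9, 0.5, 0.8, 0.8, 0.8 and 1.6.

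**IARs per 100 infusions**, which the plan does not tabulate, first three periods at p = 0.10:
- p' = 0.03: 7.02, 4.02, 3.16; decline 1 − 3.16/7.02 = 55%.
- p' = 0.05: 7.87, 5.73, 5.12; decline 35%.
- p' = 0.07: 8.72, 7.44, 7.07; decline 19%.

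At p = 0.05 or 0.20 with the same relative cuts, the decline is about 14% to 51%.

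**If premedication covers only the next infusion**, as Appendix B literally reads, p = 0.10 and p' = 0.03 give a nearly flat 9.4, 9.3, 9.3, 9.3, 9.3 and 9.3 per 100.

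**Fixed denominator.** If a fraction f of children has left before a period, the reported percentage is (1 − f) times the percentage among those still treated.

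**Splitting by a premedication flag.** Suppose half the children are susceptible (p = 0.10) and the rest never react. The rate on unpremedicated infusions is then about 3.6, 1.3 and 0.2 per 100 in the first three periods, only because reactors move to the premedicated group.

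**Precision.** With 10 children, 5/10 has an exact 95% interval of 19% to 81%, and 2/10 of 3% to 56%.

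**The case against.** A reader might infer that IARs are bound to look as if they wane. The documents do not support that. The planned metric is subjects or events over lengthening periods, and on that metric most cases above show no steady fall. A decline due to premedication also needs premedication that works and is continued past the next infusion; neither is stated. Dose escalation may push IARs up. This objection stands, and it limits the point to what the tables cannot distinguish.

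A reader might also infer that reaction-triggered premedication lowers the study-wide percentage of children with any IAR. It cannot, because a child's first IAR comes before it. Only repeat events and by-period figures are affected.

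Nor is premedication uncaptured. Drugs and reasons are recorded, infusions and IARs are listed, and further displays over time are allowed. With at most 10 children and no formal testing, someone could rebuild each history by hand. That is true and makes the matter less serious, but the reconstruction is not prespecified and would span separate listings. Neither document says that a falling count will be read as tolerance; the risk lies in leaving the table open to that reading.

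Finally, a rate split by premedication can create its own waning by selection, as shown above. That stands, and it shapes the fix.

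**Conclusion.** The point holds as a limit on interpretation. The by-period IAR table mixes period length, departures, premedication, rate slowing and dose change, and no planned display separates them. Period length alone can move the subject percentage from 49 to 93 at a constant 5% risk.

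The 19% to 55% decline is illustrative. It applies only to a per-infusion rate, at an assumed 10% starting risk, with premedication kept up after the first IAR. It is not a prediction for this study. All the risks used are assumptions, because the documents give none.

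The consequence is moderate. The primary objective is affected, but the analysis is descriptive, numbers are small, and the raw data exist.

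**What to change.** In SAP 7.2.2.2 and 7.2.1, for each period, show:

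1. children still on treatment;
2. infusions given;
3. IARs per 100 infusions, beside the planned counts;
4. the percentage of infusions with prophylactic premedication, identified from the reason for administration recorded under protocol 4.5, so that drugs given to treat a same-day IAR are not counted.

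Add a by-child, by-infusion listing or plot of IAR, premedication, infusion-rate change and dose. With at most 10 children this will be the most informative display.

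Do not present the IAR rate split by premedication as a main result. If it is shown, footnote that reactors move into the premedicated group, so the unpremedicated rate can fall by selection alone.

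The cost is SAP wording, one derived infusion-level flag and one listing, from data already required. The downsides are small cells and a flag that is only as good as the recorded reason and timing: protocol 4.5 and SAP 7.1.3.3 mention reason, duration and dates, but not clock times. No change to premedication, dosing or any other clinical rule is proposed.
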